Schedule of training sessions. All enrolled participants will be asked to complete 48 training sessions over 10 weeks. The sessions will last approximately 20-30 minutes and will be completed at home or wherever the participant can obtain computer access. If the participant has no means of accessing a computer, sessions can be completed in-person in the research laboratory. Participants will be encouraged to complete 6 sessions a week, 1 per day, to reach a total of 48 by the end of the 10-week period. While each group will complete the same number of sessions to control for possible dosage effects, the content of the sessions will vary by study group. Each condition will include 8 unique Lumosity games.

Active Cognitive Training (ACT). Sessions will include games from Lumosity that are designated as targeting working memory. One training session will be comprised of a randomly generated subset of 4 of the 8 working memory games, each played twice back-to-back.

Control Training (CON). The sessions will be in the same format as the ACT group, but will utilize other Lumosity games that do not target working memory. These games will be the same length as the working memory games and participants will complete the same number of randomly generated games per session (4 of the 8 games, played twice back-to-back).

Post-training Assessment. After completing the 48th training session, or at the end of the 10-week training window, participants will complete a post-training assessment. This 3-hour visit will occur within 1 week of the final training session and will consist of a battery identical to the baseline assessment. Alternate forms of neuropsychological tests involving memory will be used to avoid effects related to repeated testing. Participants will also complete a process measure to describe their experiences of the intervention and provide feedback on perceived benefits, barriers to completing sessions, and the length, number, and content of sessions. This assessment includes open-ended questions and ratings of satisfaction and helpfulness.

One-month Follow-up Assessment. One month after the post-training assessment, participants will complete a follow-up assessment. This 3-hour visit will consist of a battery identical to the baseline assessment. Alternate forms of neuropsychological tests involving memory will be used to avoid any effects related to repeated testing.

Human Subjects Protections

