Consent processes and documents. Prior to the initiation of any clinical research procedures, designated research staff will describe the study's purpose, all procedures, and risks/benefits and review the informed consent document with the participant. Participants will be provided ample time to read the consent, ask questions, and deliberate their decision. If they choose to participate they will then provide written informed consent. Participants will also sign a release of information form to allow study staff to review their medical record at any other facility where they have obtained HIV and/or other medical care, if applicable. Participants will be given copies of these documents. Participants will provide informed written consent for each of the two parts of the study. These documents will be stored in locked file cabinets in locked offices separate from other data collected in this study.

Compensation. Participants will receive compensation for each of the study visits. Participants may earn up to \$441. Participants will be compensated \$50 for the screening visit, \$75 for the baseline assessment, \$65 for the post-training assessment, and \$85 for the 1-month follow-up. For the 48 training sessions, participants will be compensated \$2 for each completed session, and will earn a bonus after every 6 sessions. Participants will earn a \$5 bonus after completing 6, 12, 18, and 24 sessions; a \$10 bonus after 30 and 36 sessions; and a \$15 bonus after 42 and 48 sessions. Total potential earnings for completing all sessions are \$166.

Compensation will be in the form of a reloadable debit card. In addition, we will offer bus tokens (worth \$2 for round-trip) or parking passes (worth up to \$6) to participants who require assistance.

Safety assessment. Our assessment batteries include several measures intended to assess for safety, including breathalyzer for alcohol intoxication and mental status exam. Adverse events (AEs) will be monitored throughout the study. Each AE will be classified as serious or non-serious, and appropriate reporting procedures will be followed.

Statistical analyses

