Initial analyses will confirm the psychometric properties of the assessments, and scale scores will be constructed. Data distributions will be checked to determine if they meet the assumptions of the analytic models, and transformations will be performed when necessary to improve distributional qualities. Preliminary analyses will compare study groups on demographic and other characteristics obtained in the screening and baseline assessments to identify possible failures in random assignment, which would be statistically controlled for in subsequent analyses. We will also test for any differential attrition across groups at both follow-ups. All analyses will be repeated with other substance use added as a covariate.

Hypothesis testing (Aim 1). Using an intent-to-treat analysis, we will investigate the differential impact of condition (ACT vs. CON) at the post-training assessment by performing a 2 (Condition) by 2 (Time) general linear model (GLM) analysis on the main outcome measures of working memory (mean T-score on the 3-test battery) and delay discounting (natural log k-value). Time will be a within subjects factor defined by baseline versus post-training assessment. The analysis will be repeated, adding the 1-month follow-up in a 2 (Condition) by 3 (Time) GLM to detect differential effects of the two conditions on outcomes through the follow-up period. Significant interactions of Condition and Time are predicted. To examine the specificity of the cognitive training intervention, we will use the same models to test for group differences on performance in other cognitive domains (e.g., verbal fluency, processing speed) and other measures of decision making (i.e., contingency learning, risk taking propensity).

Additional analyses will be restricted to participants who were randomized to ACT. First, we will examine predictors of treatment response (moderators) based on sample characteristics. We will use linear regression to predict change in the main outcome variables (working memory and delay discounting), with potential moderators entered separately as predictors. Second, we will use linear regression to evaluate the effect of treatment dosage (number of sessions completed) on change in the outcome variables. Finally, if intervention effects are identified on main outcomes, we will test whether effects were mediated by performance on the working memory training modules using bootstrap analyses.³⁶⁻³⁸

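### Within-ACT predictors of change are labelled moderators, and a mediator that exists only in ACT is meant to explain the ACT-CON effect; neither analysis can answer the question it is named for

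*Combined protocol and SAP*

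**What the plan says.** Under *Statistical analyses, Hypothesis testing (Aim 1)*, the intervention effect is defined as a comparison of arms, tested by the Condition x Time interaction. The next paragraph adds three analyses.

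- **Predictors.** "Additional analyses will be restricted to participants who were randomized to ACT. First, we will examine predictors of treatment response (moderators". The main outcomes are working memory and delay discounting. Change in each is regressed on sample characteristics, "with potential moderators entered separately as predictors".
- **Dosage.** "we will use linear regression to evaluate the effect of treatment dosage (number of sessions completed) on change in the outcome variables".
- **Mediation.** "if intervention effects are identified on main outcomes, we will test whether effects were mediated by performance on the working memory training modules", by bootstrap.

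For these analyses the plan names no Condition x characteristic term, no baseline covariate and no CON comparator. Two general provisions do not supply them: repeating analyses with other substance use as a covariate, and controlling for randomisation failures.

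Three other sections matter. *Control Training (CON)* says the control sessions "will utilize other Lumosity games that do not target working memory". *Post-training Assessment* says: "Alternate forms of neuropsychological tests involving memory will be used to avoid effects related to repeated testing". *Compensation* pays participants "for each completed session, and will earn a bonus after every 6 sessions", without distinction by arm.

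**The concern.** The three analyses carry names that belong to a comparison of arms or to a causal effect, but they use data that cannot support either.

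- **Moderators.** Change within ACT contains the training effect plus regression to the mean, retest gain and natural change. The last three also occur in CON. A characteristic that predicts any of them could be reported as showing who responds to ACT.
- **Mediation.** If a main effect is found, an association between game scores and change within ACT could be reported as the mechanism of the ACT-CON difference.
- **Dosage.** All participants are asked to complete the same 48 sessions, so the number completed reflects the participant's behaviour and was not randomised.

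What is at stake is the reading of these additional analyses. The two-arm Condition x Time tests are not touched.

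**Working it through.** The documents give no sample size, pre-post correlation or effect size, so there is no stated figure to reproduce. The identification arguments (steps 1 and 5) need no numbers. All rates below rest on assumed inputs.

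**1. What a within-ACT slope estimates.** Write expected change as α + τT + βx + δTx, with T = 1 for ACT and 0 for CON, and x the characteristic. The slope is β in CON and β + δ in ACT. Moderation is δ. ACT data alone give only β + δ.

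**2. Regression to the mean.** Assumptions: 20, 30 or 40 per arm, pre-post correlation r = 0.7 or 0.8, constant treatment effect 0.4 SD (so δ = 0), two-sided 5%, 20,000 simulated trials per cell. With equal variances, corr(change, baseline) = -√((1 - r)/2):

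- r = 0.7: -√0.15 = -0.387
- r = 0.8: -√0.10 = -0.316

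A characteristic correlated c with baseline, and linked to follow-up only through it, inherits c times this. For example, 0.5 x 0.387 = 0.194 in absolute value.

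Share of trials in which the ACT-only regression of unadjusted change is significant:

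| Characteristic | r = 0.7; n = 20 / 30 / 40 | r = 0.8; n = 20 / 30 / 40 |
|---|---|---|
| Unrelated to baseline | 4.9 / 5.1 / 5.0% | 5.0 / 4.8 / 5.0% |
| Correlation 0.3 with baseline | 7.7 / 9.2 / 11.2% | 6.9 / 7.8 / 8.7% |
| Correlation 0.5 with baseline | 13.3 / 17.2 / 22.6% | 10.4 / 13.5 / 16.3% |
| Baseline score itself | 40.6 / 57.8 / 70.6% | 28.4 / 40.9 / 51.8% |

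The two-arm Condition x characteristic test gave 4.7-5.3% in every cell.

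**3. Is baseline adjustment within ACT enough?** It returns the unrelated, 0.3 and 0.5 cases to 4.8-5.2%. It does not help when the characteristic predicts retest gain or natural change equally in both arms. At partial correlations of 0.2, 0.3 and 0.4 with change, the adjusted ACT-only test is significant in 13-24%, 24-47% and 41-73% of trials. The two-arm test stays near 5%.

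**4. The opposite failure.** Suppose the slope is 0 in ACT and -0.4 in CON (change with residual SD 1), so moderation is real. At 30, 50 and 100 per arm the ACT-only test is significant in 4-5% of trials, and the interaction test in 31%, 48% and 78%.

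**5. Mediation.** The indirect effect is a x b, where a is the effect of Condition on the mediator M and b is the effect of M on the outcome given Condition. There are two readings of the plan:

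- *ACT only.* Condition is constant. The design matrix [1, Condition, M] has rank 2 with 3 columns, so a cannot be estimated.
- *Both arms.* M has no value in CON. Setting it to 0 makes a depend on where the game score places its zero. In a simulation where M has no causal effect, b = 0.244 and the total effect is 0.504. Shifting the zero by 0, 1, 2, 5 or 10 units gives a = -0.013, 0.987, 1.987, 4.987 or 9.987. The proportion mediated, ab/0.504, is then -1%, 48%, 96%, 242% or 484%.

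A slope of change on M within ACT can be fitted but answers another question. With ability driving both M and change (assumed coefficient 0.3) and no causal effect of M, it is significant in 19%, 27%, 44% and 73% of trials at 20, 30, 50 and 100 in the arm.

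**6. Dosage.** If self-selection alone gives sessions and change a correlation of 0.2, 0.3 or 0.4, the ACT slope is significant in 14-24%, 25-48% or 43-74% of trials at 20-40 per arm, with no dose effect (10,000 trials per cell). A two-arm interaction stays at 4.7-5.3% here only because self-selection was assumed equal in both arms.

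**The case against.** The plan openly restricts these analyses to ACT, describes the first as predictors of response with the moderator label in parentheses, and leaves the ACT-CON question to the preceding GLM. In a feasibility and preliminary-efficacy study, predicting change within one arm is a reasonable thing to do. Much of this stands: under an accurate name the analysis is legitimate, and the dosage part is largely a matter of wording.

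Several further points are also fair.

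- Entering moderators separately means only that they are not entered jointly. That change is unadjusted is inferred from the absence of any named baseline covariate.
- The rates in steps 3 and 6 are the ordinary power of a regression to detect an association that was assumed to exist. Each is a correct finding of association, and wrong only if read as moderation or as a dose effect.
- The highest rates in step 2 are for the baseline score, which the plan does not name as a candidate. At correlation 0.3 the inflation is modest.
- Alternate test forms are a genuine attempt to limit retest effects, though they cannot remove regression to the mean.
- The two-arm interaction has low power.

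None of this rescues the labels. Low power for the right question does not justify testing a different one, and no reading of the mediation sentence makes the indirect effect of ACT versus CON estimable.

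**Conclusion.** The concern holds. As written, the plan would support moderator and mechanism statements that its analyses cannot establish. The mediation fault is one of identification: it depends on no assumed number, more participants would not cure it, and it arises only if a main effect is found. The moderator fault is equally one of logic. Its numerical size depends on the characteristic, from no inflation when it is unrelated to both baseline and shared change, to 28-71% for the baseline score, all under assumed inputs. The dosage fault is causal wording for a confounded association. These are faults in the additional analyses that should be corrected, and they leave the primary comparison intact.

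**What to change.** Reword the paragraph on additional analyses.

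- **Moderators.** Fit both arms with a Condition x characteristic term, adjusted for the baseline outcome. Report the interaction estimate with its confidence interval. Call any ACT-only regression a descriptive predictor of change, and adjust it for baseline.
- **Mediation.** Relabel the game-score analysis as a within-ACT association and draw no mediation claim from it. A mediator measured in both arms would be a separate, additional hypothesis.
- **Dosage.** Report session count as a non-randomised association, with the CON slope beside it. State that this does not remove confounding, because session content differs by arm and reasons for completing sessions may differ too.

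No new data are needed. The assessments are scheduled for all participants, and completed sessions are counted for payment.

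The cost is precision. The interaction is a difference of two independent slopes, so its standard error is about √2 = 1.41 times that of one slope with equal arms (1.42-1.44 in simulation). For an assumed true slope difference of 0.3 SD per SD, power at 20, 30 and 40 per arm is 22.5%, 34.1% and 44.0% (r = 0.7), or 30.5%, 43.3% and 56.5% (r = 0.8). Moderator results should therefore be read as estimates rather than as tests.

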Working Memory	Paced Auditory Serial Addition Test-100 ²⁵ WAIS-IV Letter-Number Sequencing, ²² WAIS-IV Digit Span ²²
Premorbid Functioning	Wechsler Test of Adult Reading (WTAR) ²⁶
Decision Making	
Decision Making	Game of Dice Task ²⁷
Delay discounting	Monetary Choice Questionnaire ²⁸
Abstract reasoning	Wisconsin Card Sorting Test-64 (WCST) ²⁹
ACASI	
Psychiatric Symptoms	Symptom Checklist 90-Revised (SCL-90) ⁶
Food Insecurity	Household Food Insecurity Access Scale ³⁰
Craving	Stimulant Craving ⁹
Quality of Life	World Health Organization Quality of Life-BREF (WHOQOL-BREF) ³¹
Self-assessment	Patient's Assessment of Own Functioning Inventory ³²
Sexual/Drug Risk	Risk Assessment Battery (RAB) ³³
Nicotine Dependence	Fagerstrom Test for Nicotine Dependence (FTND) ³⁴ and smoking history
Stimulant Dependence	Severity of Dependence Scale (SDS) ³⁵

selections will be analyzed. The Monetary-Choice Questionnaire (MCQ) is a delay discounting task. Participants make 36 choices between smaller immediate rewards (ranging from \$11 to \$78) and larger delayed rewards (ranging from \$25 to \$85 and from 7 to 186 days). An individual's point of indifference where the perceived value of a smaller immediate reward is equivalent to a larger delayed reward is computed using the following hyperbolic function: $V_{\text{immediate}} = V_{\text{delayed}} / (1 + kD)$, in which V is value in dollars, D is delay in days, and k is a free parameter that determines the discount rate. The Wisconsin Card Sorting Test-64 (WCST) is used to measure abstract reasoning, concept generation, and perseverative responding. In this computerized task, participants sort cards according to one of three principles of class membership, including categories completed, perseverative responses, perseverative errors, nonperseverative errors, failure to maintain set, and efficiency of learning.

Cognitive Training Sessions. At the end of the baseline assessment, enrolled participants will be randomly assigned to either the experimental (Active Cognitive Training, or ACT) or control (or CON) conditions using simple random assignment. Participants will be trained to use Lumosity after the baseline assessment. Research staff will provide instructions and guide them through the first training session. Participants will then immediately begin completing sessions at home the following day.

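### The ACT-only regression on sessions completed cannot be read as a dosage effect, because session count is participant behaviour; report the CON slope and the slope difference as well

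*Combined protocol and SAP*

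**What the plan says.** Under Statistical analyses, Hypothesis testing (Aim 1), the plan states: "Additional analyses will be restricted to participants who were randomized to ACT". The second of these analyses is the dosage model: "we will use linear regression to evaluate the effect of treatment dosage (number of sessions completed) on change in the outcome variables". The outcomes are the mean working-memory T-score and ln k. The sentence names no covariate, and nothing limits a causal reading of the slope. Only the mediation analysis is made conditional on finding an intervention effect; the dosage regression runs regardless.

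Participants are allocated to "conditions using simple random assignment" (Cognitive Training Sessions). Under Schedule of training sessions, the sessions "will be completed at home or wherever the participant can obtain computer access", with the laboratory as a fallback, and the pace is advisory: "Participants will be encouraged to complete 6 sessions a week, 1 per day". Compensation pays per session with rising bonuses, and Acceptability (Aim 2) counts 36 of 48 sessions as completion. The plan therefore expects the completed number to vary.

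On the role of CON, the schedule section says: "While each group will complete the same number of sessions to control for possible dosage effects, the content of the sessions will vary by study".

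Post-training Assessment gives two timing statements. The first is "After completing the 48th training session, or at the end of the 10-week training window, participants will complete a post-training assessment". The second is "This 3-hour visit will occur within 1 week of the final training session".

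**The concern.** The slope is described as an effect of dosage, but nobody is assigned a dosage. Those who complete more sessions may differ from those who complete fewer in motivation, stability, current cocaine use or starting level, and any of these could move test scores without training. An ACT-only regression cannot separate such influences from training.

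The planned adjustments do not remove the problem. Repeating all analyses with other substance use as a covariate leaves motivation and baseline score untouched. Controlling for failures of randomization addresses ACT against CON, not high against low completers within ACT.

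What is at stake is the report. A null randomized comparison could stand beside a significant dosage effect in the treated arm, with no planned caveat. CON, which shares the session format and target and would show much of the non-specific association, is not used.

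**Working it through.** The documents state no sample size, alpha, SD of change or sessions-change correlation, so there is no planned figure to reproduce. The following are assumptions: n = 20, 30 or 50 per arm, equal allocation, a two-sided 5% test, and a true training effect of zero unless stated.

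**1. False-positive chance of the ACT-only slope.** Let r be the correlation between sessions and change that arises from self-selection alone. By the Fisher z approximation, with d = atanh(r) × √(n − 3),

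P(p < 0.05) = Φ(d − 1.96) + Φ(−d − 1.96).

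Example, r = 0.3 and n = 30: d = 0.3095 × √27 = 1.608, so P = Φ(−0.352) + Φ(−3.568) ≈ 0.36.

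| r | n = 20 | n = 30 | n = 50 |
|---|---|---|---|
| 0.2 | 13% | 18% | 29% |
| 0.3 | 25% | 36% | 56% |
| 0.4 | 42% | 60% | 83% |

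Direct simulation agrees to about one percentage point (14/19/29%, 24/36/57% and 43/60/84%), which gives the overall range of about 13% to 84%.

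**2. The same question with the protocol's session cap and visit rule.** This simulation assumed a pace of mean 4.9 and SD 1.4 sessions per week, a cap of 48, a test at session 48 or week 10 plus 0 to 1 week, and an SD of change of 5 T-points. A correlation of 0.3 between engagement and natural change (about 0.20 between sessions and change) gave 14%, 19% and 30% false positives. A correlation of 0.4 (about 0.27) gave 22%, 32% and 49%. Almost all the significant slopes were positive.

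**3. Using both arms.** With equal self-selection in ACT and CON, the Sessions × Condition test stayed at 4.5% to 5.4% in every setting of that simulation. Two limits were checked by direct simulation:

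- *Unequal self-selection* (r = 0.4 in ACT, 0.1 in CON, no dose effect): the interaction is falsely significant in about 15% (n = 20) to 33% (n = 50) of trials.
- *Power* when only ACT has a real dose correlation of 0.3: about 15% to 31% for the interaction, against about 26% to 58% for the ACT-only slope. With equal arms and equal spread, the standard error of the difference is √2 ≈ 1.4 times that of one slope.

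**4. Visit timing.** At 6 a week, 48 sessions take 48/6 = 8 weeks, so the visit falls at about weeks 8 to 9. Now take a participant who stops after 24 sessions at that pace, at week 24/6 = 4. The 10-week trigger puts the visit at week 10 or later; the one-week rule puts it at week 5 or earlier. Under the first statement a low count goes with a long interval; under the second it can go with a short one.

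On the 10-week reading, with self-selection switched off, false positives were about 5% to 6% if retest gain fades by 0.25 T-points per week, 6% to 7% at 0.5, and 8%, 10% and 13% (n = 20, 30, 50) at 1.0. Adjusting the ACT-only slope for interval removed this part but left 7% to 19% false positives when engagement correlated 0.3 to 0.4 with natural change.

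**The case against.** The magnitude is conditional: it assumes a confounding correlation and then reports the chance of detecting it. That stands. The documents do not show that such a correlation exists or how large it is, so the range shows sensitivity and is not a forecast.

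The interaction is not a cure. Its 5% error rate follows from assuming equal self-selection, yet the arms play different games. It also has low power, so making it the only admissible evidence could produce an uninformative null. Both points stand and shape the fix.

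Three stronger readings are tempting, but the text does not support them:

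- *That the design ties low dose to a long retest interval.* This uses the 10-week trigger and ignores the one-week rule, which can reverse the direction for early stoppers. Even on the favourable reading, the timing bias is modest unless retest gain fades quickly. Alternate forms are planned for tests involving memory, though the plan does not say whether these include the working-memory tests.
- *That variable completion contradicts the equal-session statement.* Participants are asked to complete 48, so the statement can be read as describing the assigned schedule.
- *That the slope will be used to support efficacy or to set the dose of a later trial.* The plan says neither. It states no dose hypothesis, and efficacy rests on the intent-to-treat Condition by Time test.

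**Conclusion.** The point holds in limited form. As written, the plan can report a dosage effect when training has none, because the predictor is self-selected and the arm that could show the non-specific association is excluded. The false-positive chance is about 13% to 84% for r = 0.2 to 0.4 and n = 20 to 50 in ACT, all assumed. That a bias arises needs only that session count be correlated with natural change; its size depends on the assumptions. A CON comparison improves on the ACT-only slope but leaves the evidence exploratory. This is a cheap improvement to a secondary analysis. The visit-timing issue is a conflict to be reconciled, not an established second source of bias.

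**What to change.** In Hypothesis testing (Aim 1), replace the ACT-only dosage regression with a model in both arms: change on baseline score, Condition, sessions completed, and Sessions × Condition. Report the ACT slope, the CON slope and their difference, each with a confidence interval. State that the ACT-only slope is observational and is not read as a dosage effect, that the difference is the main but exploratory evidence, and that the favourable direction is positive for working memory and negative for ln k.

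Add days from baseline to the post-training visit as a sensitivity covariate only. It is partly determined by session count (correlation −0.53 in the simulation with the session cap), so adjusting for it costs precision.

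In Post-training Assessment, reconcile the two timing statements for participants who stop before session 48.

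The cost is SAP wording. CON session counts are already needed to pay participants. The downsides to state in the SAP are the standard error about 1.4 times larger, with the lower power shown above, and the dependence on similar self-selection in the two arms.

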COGNITIVE TRAINING TO REDUCE IMPULSIVITY IN HIV-INFECTED COCAINE USERS

NCT02909101

Study Protocol with Statistical Analysis Plan

VERSION DATE: April 13, 2018

Specific Aims

This study tests the feasibility and preliminary efficacy of a computerized cognitive training program to improve working memory and decrease impulsivity (delay discounting) among HIV-infected individuals. The specific aims are to

- (1) Investigate the effects of the cognitive training intervention on working memory (primary outcome) and delay discounting (secondary outcome) in HIV-infected persons;
- (2) Establish the acceptability of computerized cognitive training among HIV-infected past or present cocaine users; and
- (3) Examine the effect of cognitive training on HIV risk behaviors, including cocaine use, risky sex, and medication adherence (exploratory outcomes).

We hypothesize that: (1) Participants assigned to active cognitive training (ACT), compared to those in the attention-matched control group (CON), will have greater improvements in working memory and reductions in delay discounting; (2) Participants assigned to ACT, compared to those in CON, will have greater reductions in HIV risk behaviors, including improvements in medication adherence.

Study design

The proposed study will test the efficacy of a cognitive training program to improve working memory in a sample of HIV-infected cocaine users. We will evaluate the effects of this cognitive training intervention on working memory, delay discounting, and HIV risk behaviors. We will first screen participants for eligibility. Eligible participants will be assigned to one of two groups (ACT or CON) and will complete 48 training sessions over 10 weeks. Participants assigned to ACT will complete computerized games designed to enhance working memory, while those assigned to the attention-matched CON will complete games that use other brain attributes. We will be using a web-based program, Lumosity (Lumos Labs, Inc.; <http://www.lumosity.com>). Lumosity is available to the public and offers user-friendly cognitive training games targeting different brain areas. We have developed a contract with Lumosity tailoring the website to fit our study's needs. All participants will complete assessments at baseline, post-training, and 1-month follow-up to evaluate the impact of the training program. Staff members conducting assessments will be blinded to treatment condition in order to ensure no biases occur during testing.

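### The planned mediation test cannot show mediation of the ACT-versus-CON effect: condition is constant within ACT, and CON never plays the working memory modules

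*Combined protocol and SAP*

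**What the plan says.** All references are to the combined protocol and SAP.

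- **Effect under test.** Under Statistical analyses, Hypothesis testing (Aim 1), the main analysis is a Condition by Time model: "we will investigate the differential impact of condition (ACT vs. CON) at the post-training assessment".
- **Restriction.** The next paragraph opens "Additional analyses will be restricted to participants who were randomized to ACT" and lists three items: moderators of response, dosage and mediation.
- **Dosage item.** The second item is a regression to "evaluate the effect of treatment dosage (number of sessions completed) on change in the outcome variables".
- **Mediation item.** The third and last item reads: "if intervention effects are identified on main outcomes, we will test whether effects were mediated by performance on the working memory training modules". Bootstrap analyses are named as the method. The sentence names no exposure variable, and no module performance score is defined.
- **Training content.** Under Active Cognitive Training (ACT): "Sessions will include games from Lumosity that are designated as targeting working memory". Under Control Training (CON), the sessions "will utilize other Lumosity games that do not target working memory".

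**The concern.** A mediation analysis of a randomised effect needs two things: an exposure that varies (here, condition) and a mediator that exists in both arms. The plan supplies neither together. In the ACT-only population it specifies, condition is a constant. In the pooled population, the mediator is undefined for everyone in CON.

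The risk is one of interpretation. The test runs only after a positive main result, when a mechanism claim is most tempting. Within ACT, better module performance may go with greater outcome change simply because of ability or effort. Under the present wording, that association could be reported as evidence that module performance carried the intervention effect, which the analysis cannot show.

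**Working it through.** The plan gives no figure to reproduce here: no sample size, power or alpha is stated for this analysis. The question is whether the quantity can be estimated, so the check takes each possible reading in turn.

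**Set-up.** Let X be condition (ACT = 1, CON = 0), M module performance and Y the outcome (change in working memory or in ln k). The usual product-of-coefficients analysis fits

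- mediator model: M = i₁ + aX + e₁
- outcome model: Y = i₂ + c′X + bM + e₂

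and bootstraps the indirect effect a × b.

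**Reading 1: ACT only, as written.** X = 1 for everyone, so its column duplicates the intercept.

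- Mediator design [1, X]: rank 1 of 2, so a is not estimable.
- Outcome design [1, X, M]: rank 2 of 3, so c′ is not estimable. The slope b is.

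With no a, there is no a × b to bootstrap. Numerical rank checks at assumed sizes of 20, 30 and 40 per arm gave the same result each time, as they must.

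**Reading 2: both arms, observed scores only.** This takes the last item as lying outside the ACT restriction. CON does not play the working memory games. The assessment battery does not supply a score either: Table 2 lists no training game, and both follow-up batteries repeat the baseline one. M is absent for 100% of CON, complete cases include 0 CON participants, and the analysis collapses to Reading 1.

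**Reading 3: both arms, CON assigned a fixed score c.** The designs now have full rank, but the answer is built in:

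- a = (ACT mean of M) − c.
- Adjusting M for the intercept and X centres it within each arm. In CON the result is zero for everyone, so b comes entirely from ACT and equals the within-ACT slope.
- Hence indirect effect = b × (ACT mean − c), and direct effect = total effect − indirect effect.

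The following illustration uses simulated data with assumed values: 40 per arm, module score mean 50 and SD 10, true slope 0.3, true direct effect 2, residual SD 5. The realised ACT mean was 50.03, b was 0.296 and the total effect was 3.59.

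| c for CON | a = 50.03 − c | a × b | direct = 3.59 − a × b |
|---|---|---|---|
| 0 | 50.03 | 14.81 | −11.22 |
| 25 | 25.03 | 7.41 | −3.82 |
| 40 | 10.03 | 2.97 | 0.62 |
| 50 | 0.03 | 0.01 | 3.58 |
| 60 | −9.97 | −2.95 | 6.54 |

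The data, the total effect and b are the same in every row. Only the assigned value changes.

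**Reading 4: ACT only, sessions completed as exposure.** Replace X by the number of sessions S. The designs [1, S] and [1, S, M] have rank 2 of 2 and 3 of 3, so the model runs. It estimates a path from dose through performance to outcome change among people who chose how many sessions to complete. S is not randomised, and the result does not decompose ACT versus CON.

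**The case against.** The strongest counter-argument is that the plan never names condition as the exposure. The paragraph is about ACT, and the sentence just before concerns dosage, so sessions to performance to outcome is a reasonable reading, and it can be estimated. A second estimable reading relates baseline-to-post change within ACT to gain on the modules. On this view the fault is an unnamed exposure, not an impossible analysis. It is true that the exposure is unnamed. But the trigger is an intervention effect on the main outcomes, and the plan tests that effect as ACT versus CON. Neither alternative decomposes that contrast; the second is simply the within-ACT association.

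It is also fair to say that nobody has proposed filling in CON scores, and that if performance means gain, zero is a less arbitrary value than 25 or 50. That softens the illustration but does not rescue the analysis: gain on games never played is undefined, and b still rests on non-randomised variation within ACT. The tabulated figures come from invented data and say nothing about effect sizes in this trial.

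Two points stand. The module score is undefined: each session draws a random 4 of 8 games, so participants' scores rest on different mixes, and any replacement analysis needs a scoring rule. And the stakes are limited: this is a conditional analysis, last in its list, in a study of feasibility and preliminary efficacy.

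**Conclusion.** The concern holds. As written, the test cannot estimate mediation of the ACT-versus-CON effect by module performance, whether run in ACT alone or in both arms. This follows from the design, not from low power, and is the same at any sample size. It rests on two facts in the text: CON does not play the working memory games, and the effect that triggers the test is the between-arm one. What can be estimated is a within-ACT association, or a dose model with a non-randomised exposure.

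The scope is narrow. The primary Condition by Time comparison and the acceptability criteria are untouched. The wording should be changed because it would attach a causal label to an association.

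**What to change.** **Main change (SAP wording only, no new data).** Stop describing this item as a test of mediation of the intervention effect. State instead that module performance will be related to change in working memory and change in ln k within ACT, as an exploratory association with no claim about mechanism. Say how the module score is formed. If a path from sessions completed through module performance to outcome change is what is meant, name sessions as the exposure and state that it is not randomised.

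**Optional, only if mediation of the condition effect is wanted.** Use a mediator measured in both arms. One example is the post-training working memory T-score as mediator of the condition effect on 1-month ln k, in all randomised participants, adjusted for baseline working memory and baseline ln k, with the planned bootstrap and labelled exploratory. The measures are already scheduled at baseline, post-training and 1 month. The costs are that it tests a different mechanism, that it cannot address mediation of the effect on working memory (the primary outcome becomes the mediator), and that confounding between mediator and outcome, for example by effort, can remain after baseline adjustment. The main change does not depend on it.
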